# 6.3 Follow-up

		Months Following Study Treatment End (after day 150 imaging)								
Follow-up Month	Follow up visit 1 (90 days from Day 150)	Follow up visit 2 (90 days from FU-V1)	Follow up visit 3 (180 days from FU-V2)	Follow up visit 4 (180 days from FU-V3)	Follow up visit 5 (180 days from FU-V4)	Follow up visit 6 (352 days from FU-V5)	Follow up visit 7 (352 days from FU-V6)	Follow up visit 8 (352 days from FU-V7)	Study End	
Scheduling Window	+/- 14 days	+/- 30 days	+/- 30 days	+/- 30 days	+/- 30 days	+/- 30 days	+/- 30 days	+/- 30 days		
Administrative Procedures									]	
Subsequent antineoplastic therapy status	x	X	X	X	X	x	X	X		
Survival Status 	X	x	x	x	x	x	x	X	-	
Clinical Procedures and Asses	sments				I		I		1	
Adverse Events 	x	X	X	X	x	x	x	x	-	
Directed Physical Exam	x	x	X	X	x	X	x	x		
Vitals and Weight (optional)	x	x	X	X	x	X	x	x		
ECOG PS(optional)	X	x	x	X	X	X	X	X		

	Months Following Study Treatment End (after day 150 imaging)								
Follow-up Month	Follow up visit 1 (90 days from Day 150)	Follow up visit 2 (90 days from FU-V1)	Follow up visit 3 (180 days from FU-V2)	Follow up visit 4 (180 days from FU-V3)	Follow up visit 5 (180 days from FU-V4)	Follow up visit 6 (352 days from FU-V5)	Follow up visit 7 (352 days from FU-V6)	Follow up visit 8 (352 days from FU-V7)	Study End
Scheduling Window	+/- 14 days	+/- 30 days	+/- 30 days	+/- 30 days	+/- 30 days	+/- 30 days	+/- 30 days	+/- 30 days	
Laboratory Procedures/Assess	nents (local labor	atory testing):							
CBC with differential	x	x	x	x	x	X	x	x	-
Serum Chemistry Panel 	X	x	x	X	x	X	x	x	-
T3, FT4, TSH		x	X	X	X	X	x	x	
Imaging									-
Tumor Imaging (CT neck)	X	x	x		x	x	x	x	-
Correlative Study Procedures	 	I	 						
Blood for correlative studies 			x						
Patient Reported Outcomes (PI	RO)				 			 	
FACT H&N 			x		x				

1. Treatment day 1 coincides with the first day of radiation therapy. Any treatment days before will be denoted with a preceding (-) symbol.

2. The window for each visit is outlined as above. If a treatment is delayed, the following treatment must occur with the same delay. Additional treatment delay can occur with the specified scheduling window. If treatment is delayed beyond that window, treatment for that scheduled course must be held. Treatment can be resumed for the next scheduled treatment day.

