#### 8.4 Analysis Endpoints

#### 8.4.1 **Efficacy Endpoints**

Radiographic Complete response (rCR) rate: proportion of subjects in the analysis population who have a complete response on RECIST 1.1 imaging at treatment end.

PET NPV rate: proportion of subjects in the analysis population who are considered to have NPV based on Hopkins Criteria scoring at treatment end.

Pathologic complete response (pCR) rate: proportion of subjects in the analysis population who have stable disease (SD) or partial response (PR) on RECIST 1.1 imaging at treatment end, who undergo salvage surgical resection and have a complete response determined on histologic evaluation.

Overall Complete Response (CR) rate: this is a composite proportion of subjects in the analysis population with a rCR, PET NPV, and pCR. This is the primary measure of efficacy for the study.

Overall Response Rate (ORR): proportion of subjects in the analysis population who have complete response (CR) or partial response (PR) based on RECIST 1.1 imaging at treatment end.

Progression-Free Survival (PFS): time from Day -7 treatment administration to the first documented disease progression or death.

Overall Survival (OS): time from Day -7 treatment administration to death due to any cause.

Locoregional Control (LRC): time from day -7 treatment to date of local or regional relapse within the primary radiation treatment field (relapse in the head or neck region, excluding CNS recurrence).

Rate of Distant Metastases (DM): proportion of subjects in the analysis population who develop distant recurrence, as defined by recurrence outside of the primary radiation treatment field (head and neck region).

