#### 8.4.3 Statistical Methods

#### 8.4.3.1 Statistical Methods for Efficacy Analyses

The efficacy endpoints, analysis population, and statistical methods (including missing data handling) that will be employed for the efficacy analyses are presented in Table 7.

The primary endpoint is the total CR rate (composite outcome of rCR, PET NPV, and pCR) on all subjects. We have designed the study to test the hypothesis that the CR rate will be greater than 40.2% assuming a rate of 60.4%. To test this, we will use a one sample, one-sided asymptotic equality test with the null hypothesis that the total CR rate will be 40.2%. This test will result in a p-value greater than 0.05 if fewer than 21 patients respond to treatment. Secondary endpoints will include rCR, pCR, PET NPV, PFS, OS, LRC, and DM rates. For the secondary endpoints, we will only estimate confidence intervals to understand the possible range of values rather than doing formal hypothesis testing. Survival curves for PFS and OS will be constructed using the Kaplan-Meier method and 1 and 2-year survival estimates will be calculated.

Endpoint Statistical Method		Analysis Population	Missing data approach			
rCR Rate	Exact binomial method: Clopper-Pearson 95% confidence interval	FAS	Subjects with missing data are considered non-responders			
pCR Rate	Exact binomial method: Clopper-Pearson 95% confidence interval	FAS 	Subjects with missing data are considered non-responders			
CR Rate	One sample, one-sided asymptotic binomial test	FAS	Subjects with missing data are considered non-responders			
Objective Response Rate (CR + PR)	Exact binomial method: Clopper-Pearson 95% confidence interval	FAS	Subjects with missing data are considered non-responders			
PFS (RECIST 1.1) by independent radiology review	Summary statistics using Kaplan-Meier method	ASaT	Censored at last assessment date			
OS	Summary statistics using Kaplan-Meier method	ASaT	Censored at last assessment date			
LRC rate	Exact binomial method: Clopper-Pearson 95% confidence interval	FAS	Subjects with missing data are considered as disease not under control			
DM rate Exact binomial method: Clopper-Pearson 95% confidence interval		FAS	Subjects with missing data are considered as disease not under control			

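### No neck CT is scheduled between day 510 and day 870, so the Kaplan-Meier 2-year PFS (about day 723) is likely overstated for progression found only by scheduled scan

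*Combined protocol and SAP*

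**What the plan says.** Section 8.4.1 defines PFS as "time from Day -7 treatment administration to the first documented disease progression or death". Section 8.4.3.1 states: "Survival curves for PFS and OS will be constructed using the Kaplan-Meier method and 1 and 2-year survival estimates will be calculated". Table 7 specifies PFS by RECIST 1.1 under independent radiology review.

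The follow-up chart in Section 6.3 chains its visits from treatment end, starting with "Follow up visit 1 (90 days from Day 150". Every later visit is counted from the one before it: a further 90 days to the second, then 180 days to each of the third, fourth and fifth. The row "Tumor Imaging (CT neck" is marked at visits 1, 2, 3 and 5 to 8. Visit 4 has a directed physical exam but no CT. Section 7.1.2.6.2 agrees with the chart: after the scan at 1 year post-treatment, neck CT is annual. The blank cell is therefore the intended schedule and not a table-reading fault.

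Section 7.1.2.6.2 also provides for imaging when signs or symptoms suggest progression. Appendix 11.4 sets a different schedule, every 9 weeks after the first year, for subjects who stop treatment for reasons other than progression.

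**The concern.** The imaging calendar and the PFS clock have different origins. The scans are spaced from treatment end (day 150), while PFS starts on Day -7. The 1-year landmark (day 358) comes 28 days after the visit 2 scan. The 2-year landmark comes 213 days after the visit 3 scan and 147 days before the visit 5 scan.

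Kaplan-Meier on first documented progression treats the detection date as the event date. A progression on, say, day 600 that is first seen at the visit 5 scan counts as progression-free at 2 years. This error can only raise the estimate relative to the truth.

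Section 4.2.3.1 says that these secondary endpoints will be compared with historical data and, if superior, may be considered when deciding whether to take the combination further. An upward shift of several points could bear on that decision.

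**Working it through.** The plan states no expected PFS, so there is no planned figure to reproduce. The PFS rates, the hazard shapes and the share of gap events found only by scan are assumptions, shown as ranges.

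**Visit days (Section 6.3).** 150 + 90 = 240; + 90 = 330; + 180 = 510; + 180 = 690 (no CT); + 180 = 870. The gap between scheduled CTs is 870 - 510 = 360 days.

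**Landmark (Section 8.4.1).** -7 + 730 = day 723 (724 if there is no day 0).

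**Do the visit windows close the gap?** Put treatment end and visits 1 to 5 at their earliest edges (-7, -14, then -30 four times):
- treatment end: 150 - 7 = 143
- visit 1: 143 + 90 - 14 = 219
- visit 2: 219 + 90 - 30 = 279
- visit 3: 279 + 180 - 30 = 429
- visit 4: 429 + 180 - 30 = 579
- visit 5: 579 + 180 - 30 = 729

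Even then the visit 5 scan falls after the landmark.

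**Size.** On the PFS clock, day 510 is 517 days and the landmark is 730 days. Let S2 be the true 2-year PFS and f the share of events in this stretch that surface only at a scheduled scan. Then

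overstatement = f × [S(517) - S2], with S(t) = S2^((t/730)^k).

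Here k = 1 is constant hazard and k < 1 is a falling (Weibull) hazard. With k = 1 the exponent is 517/730 = 0.708.

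| True 2-year PFS | S(517), k = 1 | f = 100%, k = 1 | f = 50%, k = 1 | f = 100%, k = 0.7 | f = 100%, k = 0.5 |
|---|---|---|---|---|---|
| 60% | 69.6% | +9.6 | +4.8 | +6.9 | +5.1 |
| 70% | 77.7% | +7.7 | +3.8 | +5.6 | +4.1 |
| 80% | 85.4% | +5.4 | +2.7 | +3.9 | +2.9 |

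Overstatements are in percentage points. At f = 0 every entry is zero.

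**Scale.** At a PFS of 70% with 57 patients and no censoring, the standard error is √(0.7 × 0.3 / 57) = 6.1 points, a 95% half-width of about 12 points. The worst case is a little more than one standard error.

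**The case against.** The strongest reply is that the gap concerns scheduled scans only. Visit 4, 33 days before the landmark, has a physical exam. Symptoms trigger imaging at any time, and deaths keep their own dates. The required scan covers only the neck, so distant progression may be missed whatever the timing. All of this stands. The f = 100% column is therefore a ceiling, because it requires that no PFS event of any kind be dated between days 510 and 723. It does not remove the problem: Table 7 defines PFS by radiology review, so progression suspected at the visit 4 exam still needs an image to count.

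A reader might infer that LRC is overstated in the same way, since Section 8.4.1 defines it as a time from Day -7. The documents do not support that. Section 8.4.3.1 limits Kaplan-Meier to PFS and OS, and Table 7 analyses LRC as an exact binomial proportion with missing data counted as not controlled. That rule lowers the estimate: a true 80% with 10% missing reads 0.8 × 0.9 = 72%. No rule for 2-year status is given, so the direction of any bias is undetermined.

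A reader might also infer that the comparison with historical data must favour the regimen. That depends on scan schedules and estimators in the historical studies, which the plan does not describe.

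Finally, PFS is secondary, is reported without a formal test, and has no go/no-go threshold. That limits the weight of the point but does not justify an uncorrected figure.

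**Conclusion.** The point holds for PFS. The 2-year landmark lies inside a 360-day stretch without a scheduled neck CT, and the planned estimator dates scan-detected progression in that stretch after the landmark. The Kaplan-Meier 2-year PFS is likely overstated, by between zero and about 10, 8 or 5 points at an assumed true 60, 70 or 80%. With a falling hazard the ceiling at 70% is about 4 to 6 points. The true size depends on how many gap events surface through death or symptom-triggered imaging, which the documents do not say.

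Three stronger readings are not supported: that no scan at all will take place in the gap, that the overstatement is certain or has a known size, and that it applies to LRC. The change is worth making for a secondary endpoint that may inform whether development continues.

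**What to change.** - Report Kaplan-Meier PFS at a scan-aligned time just after the visit 5 window, for example day 870 + 30 = 900, labelled as about 2 years after treatment end. Because visits are chained, some visit 5 scans may drift later, so the actual scan dates should be reported.
- Keep the day 723 Kaplan-Meier estimate for comparison with historical data, since those studies may have dated progression in the same way. State that it is likely biased upward.
- Record the last negative and first positive assessment date for each patient. Add a parametric (for example Weibull) interval-censored estimate of 2-year PFS as a sensitivity analysis. A nonparametric interval-censored estimate alone is not enough: for events known only to lie between days 510 and 870, it does not determine PFS inside the gap.
- Reconcile the imaging schedules in Section 6.3, Section 7.1.2.6.2 and Appendix 11.4. For subjects who stop treatment without progression, the appendix implies about five scans in the gap (360/63 = 5.7) where the chart has none.

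The cost is SAP wording, two date fields and a little more analysis. The scan-aligned estimate refers to a later time and will be somewhat lower: at a true 2-year PFS of 70% with constant hazard, day 900 (907 days on the PFS clock) gives 0.7^(907/730) = 64%. The sensitivity estimate depends on its parametric model.

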#### 4.2.3 **Rationale for Endpoints**

#### 4.2.3.1 Safety and Efficacy Endpoints

Safety and efficacy are the primary endpoints for this study. Safety is an important endpoint for a study like this for a number of factors. First of all, the inflammatory events surrounding chemoradiation, while potentially allowing for improved immune clearance with pembrolizumab, may end up causing more toxicity. The PD-1: PD-L1 pathway is important in normal, healthy individuals in protecting from autoimmunity during inflammatory events. As CRT will induce an inflammatory event in the head and neck region, one can surmise that PD-L1 and PD-1 upregulation may be a normal response meant to protect from autoimmune events. Evaluation of safety during and following this period is paramount to understanding the role of PD-1 inhibitors combined with CRT. While a certain level of toxicity is expected with this combination, special attention will be paid to immune-related toxicities and exacerbation of known CRT related toxicities. If this combination is not felt to be safe, it would not be recommended to move forth with further evaluation.

Efficacy is the co-primary endpoint for the study. This endpoint is important to estimate the clinical benefit of this combination. If there is little to no added benefit with this combination, it would not be recommended to move forth with additional studies utilizing this combination. If the treatment is efficacious, it would be reasonable to consider phase III testing of this combination, comparing it to high-dose bolus cisplatin.

Complete response rate was chosen as the primary efficacy measure. While progression-free survival may be a reasonable alternative to this efficacy measure, complete response rate was chosen based on several factors. First, this was the efficacy measure in preclinical studies that suggested this combination was efficacious. Second, this outcome can be compared to the Intergroup Trial [13], which evaluated high-dose bolus cisplatin in a phase III setting. In this study, imaging and clinical response were used to determine response rate. The complete response rate in those treated with high-dose bolus cisplatin was 40.2% among 87 analyzable patients. While the imaging and response criteria from that study does not directly match what

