## 5.2.1.2.3 Dose Modification for Radiation

Reversible radiation mucositis is expected to develop in the majority of patients. This will commonly manifest as Grades I to III in severity. In those rare cases of Grade IV mucositis, radiation can be interrupted for up to5 consecutive radiation treatment days until the reaction subsides to Grade III. However, every effort should be made to keep this treatment break as short as possible. If Grade IV mucositis occurs, systemic chemotherapy should also be held until the reaction subsides to Grade III and then radiation and chemotherapy are resumed.

Toxicities: Common radiation toxicities include mucositis, fatigue, weight loss, regional alopecia, xerostomia, hoarseness, transient ear discomfort, hypogeusia, dysgeusia, dysphagia, and skin erythema and desquamation within the treatment fields. Less common long-term radiation toxicities include hypothyroidism, loss of hearing, chronic swallowing dysfunction requiring permanent feeding tube, and cervical fibrosis. Much less common radiation toxicities include mandibular osteoradionecrosis (<5% incidence with attention to a full dental evaluation as part of pre-treatment planning), and cervical myelopathy (<1% with restriction of spinal cord dose to < 45 Gy).

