13. Patients with residual disease (SD, PR, or PD) on post-treatment imaging will undergo salvage surgical resection (at the discretion of the surgeon) if their disease is felt curable with salvage surgery. Additionally, patients with a CR and clinical suspicion for viable residual disease will be offered salvage surgery. Following pathology analysis, salvage surgical tissue will be sent for correlative studies. Detailed instructions for tissue collection, processing, and shipment are included in the procedures manual.

14. PET imaging at baseline and treatment end is not required for the study, but is allowed for use to determine complete response rate when tumor response on standard imaging cannot confirm CR based on RECIST 1.1. Please see sections 7.1.2.6.2 and 7.1.2.6.3 for details.

15. Screening labs completed within 7 days (168 hours) of treatment initiation (day -7) will not need to be repeated.

16. Once a subject experiences confirmed disease progression or starts a new anti-cancer therapy, the subject moves into the Survival Follow-Up Phase. These subjects will be followed every 6 months to assess for survival status until death, withdrawal of consent, or the end of the study, whichever occurs first.

17. If a subject discontinues pembrolizumab, return visit timing is left to treating physician discretion until day 150 although it is highly recommended that the subject return for Day 78, 120, and 150 so research specimens and QOL can be collected.

18. Minimum interval between pembrolizumab doses is 14 days.

19. Vital signs and weight do not need to occur on the same day as the visit but need to be completed within the window and prior to the next treatment.

20. Once a subject transitions to follow-up all documented AEs will be followed until resolution or to a new baseline as determined by the treating investigator. Only new AEs that could be considered an ECI or irAR will be documented and followed while in follow-up.

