#### 7.1.2 Clinical Procedures/Assessments

#### 7.1.2.1 Adverse Event (AE) Monitoring

The investigator or qualified designee will assess each subject to evaluate for potential new or worsening AEs as specified in the Trial Flow Chart and more frequently if clinically indicated. Adverse experiences will be graded and recorded throughout the study according to NCI CTCAE Version 4.0 (see Section 11.2). Toxicities will be characterized in terms regarding seriousness, causality/attribution, toxicity grading, and action taken with regard to trial treatment.

AEs should be assessed up to 30 days following cessation of treatment and followed for 90 days for SAEs, even if the patient transitions to follow-up during this time. Once a subject transitions to follow-up all documented AEs will be followed until resolution or to a new baseline as determined by the treating investigator. Only new AEs that could be considered an ECI or irAR will be documented and followed while in follow-up.

All AEs of unknown etiology associated with pembrolizumab exposure should be evaluated to determine if it is possibly an event of clinical interest (ECI) of a potentially immunologic etiology (termed immune-related adverse events, or irAEs); see the separate ECI guidance document regarding the identification, evaluation and management of potential irAEs.

Please refer to section 7.2 for detailed information regarding the assessment and recording of AEs.

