#### 7.1.4 **Other Procedures**

#### 7.1.4.1 Withdrawal/Discontinuation

When a subject discontinues/withdraws prior to active trial completion, the subject will need to sign a withdrawal consent. If the subject becomes cognitively impaired while on this study the subject and/or their Legal Representative will have the opportunity to sign a withdrawal consent. All applicable activities scheduled for the final trial visit should be performed at the time of discontinuation/withdrawal. Any adverse events which are present at the time of discontinuation/withdrawal should be followed in accordance with the safety requirements outlined in Section 7.2 - Assessing and Recording Adverse Events. After discontinuing treatment following completion, subjects should return to the site for a Safety Follow-up Visit (described in Section 7.1.5.) and then proceed to the Follow-Up Period of the study (described in Section 7.1.5.4).

Subjects will have the option to withdraw from the study completely or partially which will allow following for progression/survival.

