#### 7.1.5.4 Safety Follow-Up Visit

The mandatory Safety Follow-Up Visit should be conducted approximately 30 days after the last dose of trial treatment or before the initiation of a new anti-cancer treatment, whichever comes first, for those subjects who do not complete active treatment. All AEs that occur prior to the Safety Follow-Up Visit should be recorded. Subjects with an AE of Grade > 1 will be followed until the resolution of the AE to Grade 0-1, return to baseline, or until the beginning of a new anti-neoplastic therapy, whichever occurs first. SAEs that occur within 90 days of the end of treatment or before initiation of a new anti-cancer treatment should also be followed and recorded.

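### Once the 30-day AE and 90-day SAE windows close, new non-immune late chemoradiation toxicity has no recording rule, and the protocol disagrees with itself on whether completers have a safety visit

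*Combined protocol and SAP*

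**What the plan says.** Safety and tolerability of pembrolizumab with chemoradiotherapy is the first primary objective (section 3.1). Section 4.2.3.1 says that "special attention will be paid to immune-related toxicities and exacerbation of known CRT related toxicities". Section 5.2.1.2.3 names the late effects to expect: "Less common long-term radiation toxicities include hypothyroidism, loss of hearing, chronic swallowing dysfunction requiring permanent feeding tube, and cervical fibrosis". It adds osteoradionecrosis (below 5%) and cervical myelopathy (below 1%) as rarer ones.

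The recording rules are as follows.

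- **Flow chart, footnote 20** (attached to the AE row of section 6.3, and repeated in 7.1.2.1): "Only new AEs that could be considered an ECI or irAR will be documented and followed while in follow-up". Events already on record continue: "Once a subject transitions to follow-up all documented AEs will be followed until resolution or to a new baseline".
- **Section 7.1.2.1**: "AEs should be assessed up to 30 days following cessation of treatment and followed for 90 days for SAEs". The same sentence goes on to say that this applies even when the subject has already moved into follow-up. Sections 1.0 and 7.2 repeat the 30-day window.
- **Section 7.2.3.1**: SAEs are reported whatever their cause until 90 days after treatment ends or new anti-cancer therapy starts. Outside that period, only SAEs judged related to the Merck product are reportable.

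On the safety visit, section 7.1.4.1 says: "After discontinuing treatment following completion, subjects should return to the site for a Safety Follow-up Visit". Section 7.1.5.4 makes the visit mandatory at about 30 days after the last dose, but "whichever comes first, for those subjects who do not complete active treatment". The flow chart has no column for it.

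**The concern.** The late effects of chemoradiation are the ones an added checkpoint inhibitor might worsen, and section 4.2.3.1 names that worsening as a focus. Section 4.2.3 also treats late morbidity as a reason to look beyond high-dose cisplatin. Yet at eight visits that already carry an AE item and a directed examination, a new non-serious fibrosis or hearing loss would not be written down unless the site thought it could be immune-related.

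The later SAE rule does little to fill the gap. Table 6 directs the investigator away from a Merck-product relationship when another obvious cause exists, and 70 Gy to the neck is such a cause for osteoradionecrosis or fibrosis. A worsened radiation toxicity would therefore tend to be classed as unrelated and drop out after 90 days.

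At stake is how the safety result is read. Section 4.2.3.1 makes further development depend on the combination being judged safe, and a small count of late events could be taken as reassurance when it was partly produced by the rule.

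The second matter is narrower. If completers have no safety visit, no scheduled contact falls at the end of their 30-day AE window.

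**Working it through.** No sample-size or power figure is involved. The check is date arithmetic on the protocol's own schedule, counted from the first day of radiation as day 1.

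**Inputs.** The last pembrolizumab dose is day 141, window -3/+7, so days 138 to 148 (sections 5.2 and 6.2). The treatment-end visit is day 150, window -7/+14, so days 143 to 164 (6.2). Follow-up intervals are 90, 90, 180, 180, 180, 352, 352 and 352 days, with visit 1 at ±14 days (6.3). AE and SAE windows are 30 and 90 days (7.1.2.1, 7.2.3.1).

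**Windows, counted from the last dose**

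- All AEs: 141 + 30 = day 171 (138 + 30 = 168 to 148 + 30 = 178).
- SAEs: 141 + 90 = day 231 (228 to 238).

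**Visits around the windows**

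- The day-150 visit is 150 − 141 = 9 days after the last dose. With both windows stretched it is at most 164 − 138 = 26 days after, still short of 30.
- Follow-up visit 1 is 150 + 90 = day 240 (226 to 254). That is 240 − 171 = 69 days after the AE window closes (range 226 − 178 = 48 to 254 − 168 = 86).
- So no flow-chart visit falls at the end of the 30-day window, or within 48 days after it. Only the visit on which 7.1.4.1 and 7.1.5.4 disagree would do so for completers.

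**Length of the unrecorded period**

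- Follow-up after day 150: 90 + 90 + 3 × 180 + 3 × 352 = 1,776 days, ending on day 1926.
- New non-serious, non-immune events: 1926 − 171 = 1,755 days, which is 1,755 / 1,776 = 99% of scheduled follow-up, or 1,755 / 365.25 = 4.8 years.
- Serious events not attributed to the Merck product: 1926 − 231 = 1,695 days, or 1,695 / 365.25 = 4.6 years.

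**Sensitivity to the meaning of cessation.** If treatment is taken to cease at day 150, which the flow chart labels treatment end, the windows close on days 180 and 240. The non-serious gap is then 1926 − 180 = 1,746 days, again about 4.8 years. Visit 1 would coincide nominally with the end of the SAE window.

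**Scale of events.** The only late-toxicity incidence above 1% that the protocol gives is below 5%, for osteoradionecrosis. In 57 subjects the ceiling is 57 × 0.05 = 2.85, about 3 cases. It is a ceiling because the stated figure is an upper bound, some cases would start before day 171 or be reported as related SAEs, and subjects who progress or start new therapy move to survival follow-up (footnote 16).

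**The case against.** A reader looking at footnote 20 alone might infer that from day 150 only immune-type events are recorded, that completers' AEs late in the 30-day window are lost, and that most of the SAE window is uncovered because no visit falls in it. The documents do not support this. Section 7.1.2.1 keeps both windows open after transition to follow-up. An event with onset before day 171 can still be entered at visit 1, which has an AE item. SAE reporting is triggered by the event, within 24 hours, so days without a visit are not lost data. Nor is the safety visit plainly absent: 7.1.4.1 provides it for completers, and 7.1.1.5.3 mentions a 30-day safety visit without limiting it to non-completers. This is a contradiction, not an established omission.

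The stronger objection is one of scope. Section 7.2 describes collection of acute events, and no objective names late CTCAE toxicity. Long-term morbidity is addressed through quality of life at 1 and 2 years, with FACT H&N at follow-up visits 3 and 5 covering dry mouth, swallowing, voice and pain. Radiation ends near day 50, so events starting within roughly 171 − 50 = 121 days are captured and then followed. Many subjects who need a feeding tube will already have it on record. New hypothyroidism may count as a possible immune event; the list that would settle this is in a separate guidance document. A single-arm trial of 57 could not firmly attribute late toxicity to pembrolizumab even with full capture.

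All of that stands, and it limits the point. It does not remove it. Symptom scores are not graded events, and describing the late toxicity of the combination is a more modest aim than attributing it. The visits and examinations where it could be described are already scheduled.

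**Conclusion.** The concern holds in limited form. After about day 171 for non-serious events, and about day 231 for serious events not attributed to the Merck product, new non-immune late chemoradiation toxicity has no recording rule for the remaining 4.8 and 4.6 years of scheduled visits. The trial therefore cannot describe late toxicity of the combination by CTCAE grade, and a low late rate would partly reflect the rule. Separately, the sections disagree on the safety visit for completers, the flow chart omits it, and footnote 20 leaves out the windows that 7.1.2.1 preserves.

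This does not mean that late toxicity is missed altogether: early-onset events are followed, and related SAEs are reportable at any time. The number of unrecorded cases cannot be estimated from the documents; about 3 osteoradionecrosis cases is an upper limit.

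The dates assume the nominal schedule with the stated visit windows and a last dose on day 141. Subjects who stop earlier have earlier windows. The conclusion does not depend on whether cessation means the last dose or day 150.

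**What to change.** 1. Amend footnote 20 and section 7.1.2.1 so that the AE item at follow-up visits 1 to 8 also records new treatment-related Grade 3 or higher AEs and the late radiation toxicities already listed in 5.2.1.2.3. Say that treatment-related covers pembrolizumab, cisplatin and radiation, because Table 6 asks only about the Merck product.
2. Write the 30-day AE and 90-day SAE windows from 7.1.2.1 into footnote 20, and define cessation of treatment as either the last dose or day 150.
3. Reconcile 7.1.4.1 with 7.1.5.4 on whether completers have the 30-day safety contact, and show the outcome in the flow chart.

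The cost is a wording amendment, a short checklist at visits that already take place and, depending on how item 3 is resolved, one contact per completer. If the sponsor prefers to leave late toxicity out of scope, the study report should say that new non-immune late events were not collected, so that their absence is not read as a low rate.
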